7.4.4 Management Algorithms for Immuno-Oncology Agents

Immuno-oncology (I-O) agents are associated with AEs that can differ in severity and duration than AEs caused by other therapeutic classes. Nivolumab, ipilimumab, and BMS-986237 are

considered immuno-oncology agents in this protocol. Early recognition and management of AEs associated with immuno-oncology agents may mitigate severe toxicity. Management Algorithms have been developed to assist investigators in assessing and managing the following groups of AEs:

- Gastrointestinal
- Renal
- Pulmonary
- Hepatic
- Endocrinopathy
- Skin
- Neurological
- Myocarditis

The above algorithms are found in the [Appendix 8](#) of this protocol.

7.4.5 Treatment of Related Infusion Reactions

Since study treatment contains only human immunoglobulin protein sequences, it is unlikely to be immunogenic and induce infusion or hypersensitivity reactions. However, if such a reaction were to occur, it might manifest with fever, chills, rigors, headache, rash, pruritus, arthralgias, hypotension, hypertension, bronchospasm, or other allergic-like reactions. All Grade 3 or 4 infusion reactions should be reported within 24 hours to the study medical monitor and reported as an SAE if it meets the criteria. Infusion reactions should be graded according to NCI CTCAE (Version 4.0) guidelines.

Treatment recommendations are provided below and may be modified based on local treatment standards and guidelines, as appropriate:

For Grade 1 symptoms: (mild reaction; infusion interruption not indicated; intervention not indicated):

- Remain at bedside and monitor participant until recovery from symptoms. The following prophylactic premedications are recommended for future infusions: diphenhydramine 50 mg (or equivalent) and/or acetaminophen/paracetamol 325 to 1000 mg at least 30 minutes before additional administrations.

For Grade 2 symptoms: (moderate reaction required therapy or infusion interruption but responds promptly to symptomatic treatment [(eg, antihistamines, non-steroidal anti-inflammatory drugs, narcotics, corticosteroids, bronchodilators, IV fluids); prophylactic medications indicated for ≤ 24 hours]):

- Stop the study treatment infusion, begin an IV infusion of normal saline, and treat the participant with diphenhydramine 50 mg IV (or equivalent) and/or acetaminophen/paracetamol 325 to 1000 mg; remain at bedside and monitor participant until

resolution of symptoms. Corticosteroid and/or bronchodilator therapy may also be administered as appropriate. If the infusion is interrupted, then restart the infusion at 50% of the original infusion rate when symptoms resolve; if no further complications ensue after 30 minutes, the rate may be increased to 100% of the original infusion rate (**for Arm B subjects**) or to 50% of the original infusion rate (**for Arm A subjects**) until completion of the infusion. Monitor participant closely. If symptoms recur, then no further study treatment will be administered at that visit.

- For future infusions, the following prophylactic premedications are recommended: diphenhydramine 50 mg (or equivalent) and/or acetaminophen/paracetamol 325 to 1000 mg should be administered at least 30 minutes before infusions. If necessary, corticosteroids (up to 25 mg of hydrocortisone or equivalent) may be used

For Grade 3 or 4 symptoms: (severe reaction, Grade 3: prolonged [ie, not rapidly responsive to symptomatic medication and/or brief interruption of infusion]; recurrence of symptoms following initial improvement; hospitalization indicated for other clinical sequelae (eg, renal impairment, pulmonary infiltrates). Grade 4: Life-threatening; pressor or ventilatory support indicated):

- Immediately discontinue infusion of study treatment. Begin an IV infusion of normal saline and treat the participant as follows: Recommend bronchodilators, epinephrine 0.2 to 1 mg of a 1:1000 solution for subcutaneous administration or 0.1 to 0.25 mg of a 1:10,000 solution injected slowly for IV administration, and/or diphenhydramine 50 mg IV with methylprednisolone 100 mg IV (or equivalent), as needed. Participant should be monitored until the Investigator is comfortable that the symptoms will not recur. Study treatment will be permanently discontinued. Investigators should follow their institutional guidelines for the treatment of anaphylaxis. Remain at bedside and monitor participant until recovery of the symptoms

In case of late-occurring hypersensitivity symptoms (eg, appearance of a localized or generalized pruritus within 1 week after treatment), symptomatic treatment may be given (eg, oral antihistamine or corticosteroids).

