7.4 Dosage Modification

7.4.1 Dose Delay Criteria

Regardless of whether or not the event is attributed to nivolumab, ipilimumab, or BMS-986237, all study treatments must be delayed until treatment can resume. Tumor assessments for all participants should continue as per protocol even if dosing is delayed.

Nivolumab, ipilimumab, and BMS-986237 administration should be delayed for the following:

- Grade 2 non-skin, drug-related adverse event, with the exception of fatigue
- Grade 2 drug-related creatinine, AST, ALT and/or Total Bilirubin abnormalities
- Grade 3 skin, drug-related adverse event
- Grade 3 drug-related laboratory abnormality, with the following exceptions:
 - Grade 3 lymphopenia or asymptomatic amylase or lipase does not require dose delay
 - Grade ≥ 3 AST, ALT, Total Bilirubin will require dose discontinuation (see [Section 7.4.3](#))
- Any adverse event, laboratory abnormality, or intercurrent illness which, in the judgment of the investigator, warrants delaying the dose of study medication.

Participants who require delay of study treatment should be re-evaluated weekly or more frequently if clinically indicated and resume study treatment dosing when re-treatment criteria are met.

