7.4.2 Criteria to Resume Treatment

Participants may resume treatment with study treatment when the drug-related AE(s) resolve to Grade \leq 1 or baseline value, with the following exceptions:

- Participants may resume treatment in the presence of Grade 2 fatigue
- Participants who have not experienced a Grade 3 drug-related skin AE may resume treatment in the presence of Grade 2 skin toxicity
- For participants with Grade 2 AST, ALT and/or Total Bilirubin abnormalities, dosing may resume when laboratory values return to baseline and management with corticosteroids, if needed, is complete.
- Participants with combined Grade 2 AST/ALT AND total bilirubin values meeting discontinuation parameters (Section 7.4.3) should have treatment permanently discontinued.
- Drug-related pulmonary toxicity, diarrhea or colitis or myocarditis myositis, rhabdomyolysis must have resolved to baseline before treatment is resumed. Participants with persistent Grade 1 pneumonitis after completion of a steroid taper over at least 1 month may be eligible for retreatment if discussed with and approved by BMS Medical Monitor.

Participants with drug-related endocrinopathies adequately controlled with only physiologic hormone replacement may resume treatment after consultation with the BMS Medical Monitor. Adrenal insufficiency requires discontinuation regardless of control with hormone replacement.

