7.4.3 Dose Discontinuation

The assessment for discontinuation of nivolumab should be made separately from the assessment made for discontinuation of ipilimumab. Although there is overlap among the discontinuation criteria, if discontinuation criteria are met for ipilimumab but not for nivolumab, treatment with nivolumab may continue if ipilimumab is discontinued. In this instance, the patient would be considered off part 1 of the study and must have a 6 weeks interval before moving on to part 2 of the study (nivolumab monotherapy).

If a participant in any of the nivolumab/ipilimumab combination arms meets criteria for discontinuation and investigator is unable to determine whether the event is related to both or one study drug, the participant should discontinue both nivolumab and ipilimumab and be taken off the treatment phase of the study.

Study treatment should be permanently discontinued for the following:

- Any Grade 2 drug-related uveitis, eye pain or blurred vision that does not respond to topical therapy and does not improve to Grade 1 severity within the re-treatment period OR requires systemic treatment
- Any Grade 3 non-skin, drug-related adverse event lasting $>$ 7 days, or recurs with the following exceptions for laboratory abnormalities, diarrhea, colitis, neurologic toxicity, drug-related

uveitis, pneumonitis, bronchospasm, myositis, myocarditis, rhabdomyolysis, hypersensitivity reactions, infusion reactions, and endocrinopathies:

- Grade 3 drug-related, diarrhea, colitis, neurologic toxicity, uveitis, pneumonitis, bronchospasm, myositis, myocarditis, rhabdomyolysis, hypersensitivity reaction, or infusion reaction of any duration requires discontinuation
- Grade 3 drug-related endocrinopathies, adequately controlled with only physiologic hormone replacement do not require discontinuation. Adrenal insufficiency requires discontinuation regardless of control with hormone replacement.
- Grade 3 drug-related laboratory abnormalities do not require treatment discontinuation except:
 - ◆ Grade 3 drug-related thrombocytopenia > 7 days or associated with bleeding requires discontinuation
 - ◆ Any drug-related liver function test (LFT) abnormality that meets the following criteria requires discontinuation:
 - Grade \geq 3 drug-related AST, ALT or Total Bilirubin requires discontinuation*
 - Concurrent AST or ALT > 3 x ULN and total bilirubin > 2x ULN

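### Protocol 7.4.5 stops dosing only for that visit when a Grade 2 infusion reaction recurs after restart, yet the same section lists such recurrence as Grade 3, which requires permanent discontinuation

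*Protocol*

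**What the plan says.** Protocol 7.4.5 sets out the management of infusion reactions by grade.

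- **Grade 2.** Stop the infusion, treat, and restart at 50% of the rate when symptoms resolve. After 30 minutes without complications, Arm B may return to the full rate; Arm A is capped at 50%. Then: "If symptoms recur, then no further study treatment will be administered at that visit". The following bullet begins: "For future infusions, the following prophylactic premedications are recommended".
- **Grade 3 or 4.** The Grade 3 description includes "recurrence of symptoms following initial improvement". The action is: "Study treatment will be permanently discontinued".
- **Reporting.** "All Grade 3 or 4 infusion reactions should be reported within 24 hours to the study medical monitor".

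Three other sections apply according to the grade. Protocol 7.4.3 says of Grade 3 drug-related events that an "infusion reaction of any duration requires discontinuation". Protocol 7.4.1 requires a delay for a "Grade 2 non-skin, drug-related adverse event, with the exception of fatigue". Protocol 7.4.2 then allows dosing again: "Participants may resume treatment with study treatment when the drug-related AE(s) resolve to Grade" 1 or below, or to baseline.

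**The concern.** The event in question is a Grade 2 reaction that settles after interruption and returns after restart. Someone reading down the Grade 2 heading finds a stop limited to the visit, followed at once by advice for later infusions. Nothing there says that the recurrence changes the grade or ends treatment. The rule that does so stands under a different heading.

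What is at stake is first participant safety: giving a further dose after a reaction that the protocol itself treats as severe. The second stake is oversight. Protocol 5.1.1 provides no data monitoring committee, so safety review rests on the medical monitor and the sponsor's safety team, and the 24-hour report applies to Grade 3 and 4 reactions only. An event left at Grade 2 would also stay out of the Grade 3-5 AE rates, the second and third secondary endpoints. Acute reactions to the infusion are the subject of the primary objective, so the instructions for managing them should be clear.

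**Working it through.** The plan gives no figure for this event, so the check sets the texts side by side.

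1. **Does the event meet the Grade 3 wording?** Restart is allowed only once symptoms have resolved. A recurrence after restart therefore always follows improvement, and it meets "recurrence of symptoms following initial improvement".
2. **What does each heading lead to?**

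| Question | Kept under the Grade 2 heading | Moved to the Grade 3 heading |
|---|---|---|
| Rest of this infusion | Not given | Not given |
| Later doses | Given with premedication; if the event is non-skin and drug-related, delayed under 7.4.1 and resumed under 7.4.2 | None under 7.4.5; discontinuation also required by 7.4.3 if drug-related |
| 24-hour report to the medical monitor | Not triggered | Triggered |
| Grade 3-5 AE rates | Not counted | Counted |

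3. **Is there a bridging sentence?** Neither 7.4.5 nor 7.4.3 has one. Section 7.4.3 does not mention recurrence after restart; it applies because 7.4.5 describes that recurrence as Grade 3.
4. **What does one case decide?** Part 1 has 4 doses, so a case at cycle k leaves 4 − k combination doses: 3, 2, 1 or 0 for cycles 1 to 4. Part 2 nivolumab may also be lost. This is not automatic in Arm B, because 7.4.3 assesses nivolumab and ipilimumab separately and lets nivolumab continue in Part 2, after a 6-week interval, if only the ipilimumab criteria are met. If the investigator cannot tell which drug is responsible, both stop.
5. **Effect on a secondary endpoint.** With 50 treated participants per arm, one event recorded as Grade 3 instead of Grade 2 moves that arm's Grade 3-5 AE rate by 1/50 = 2 percentage points, provided the participant has no other Grade 3-5 AE.
6. **Effect on the primary endpoint.** A participant counts once if at least one listed term begins on the day of an infusion or within 2 days after it. If the first reaction is coded to a listed term, the participant already counts and the recurrence adds nothing. The count could change only if the first reaction is coded outside the list, or through exposure to later doses.

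**The case against.** The strongest reply is that the texts fit together. Section 7.4.5 requires CTCAE v4.0 grading, and its own definition makes the recurrence Grade 3. The sentence limited to the visit is then an immediate stop order, and the premedication bullet no longer applies because the participant has left the Grade 2 heading. On this view 7.4.3 holds no separate conflict, and 7.4.1 and 7.4.2 come into play only if the site under-grades the event. Section 9 also requires immediate safety concerns to be discussed with the sponsor, including whether treatment should continue.

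Much of this stands. The reconciliation is possible and is probably what was meant. It is nowhere stated, however, and limiting the stop to one visit would serve no purpose if permanent discontinuation always followed. Section 7.4.5 also presents its treatment text as recommendations open to local modification, while 7.4.3 gives no such latitude for infusion reactions. The general duty in Section 9 does not correct a specific instruction that points the other way.

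It is also right that the recurrence sentence assigns no grade. Reporting and the Grade 3-5 rates follow the grade recorded. The sentence makes under-grading easier, but does not by itself decide either of them.

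**Conclusion.** The gap is real and worth correcting on safety grounds. It rests on the wording alone: the recurrence meets the protocol's own Grade 3 description, and no sentence takes the participant out of the Grade 2 instructions.

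Three stronger readings are tempting but not supported.

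- **A count of affected participants.** A reader might apply the 3.2% hypersensitivity/infusion reaction rate cited in Protocol 7.1.1: 0.032 × 50 = 1.6 per arm. That is an expected number at another study's rate, not a ceiling. Section 10.1 describes that study's regimen as nivolumab 1 mg/kg with ipilimumab 3 mg/kg, and Arm A is a new co-formulated product. Section 7.1.1 adds that no Grade 3 or 4 reactions were observed there. The documents give no share of reactions that recur after restart. Few cases are likely, but the number cannot be estimated.
- **Bias between arms.** Only Arm B may return to the full rate, so recurrences could differ by arm. Nothing in the documents shows that they would, or that sites would handle them differently by arm.
- **Harm to the primary analysis.** The primary count is usually unchanged. The Grade 3-5 rates are descriptive, and SAP 7.1 plans no p-values.

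**What to change.** In Protocol 7.4.5, replace the recurrence sentence with: *If symptoms recur after restart, stop the infusion, grade the reaction as Grade 3, report it within 24 hours, and follow the Grade 3 instructions below and Section 7.4.3 (in Arm B, the separate assessment of nivolumab and ipilimumab in 7.4.3 applies).* Limit the premedication bullet that follows to participants whose symptoms did not recur after restart. If the sponsor does intend re-dosing after recurrence, it should state that exception in both 7.4.5 and 7.4.3.

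The cost is a protocol amendment with the ethics approval described in Appendix 2. No participants or visits are added and infusion rates stay as they are. The clinical downside is that a participant with a mild recurrence loses further doses, up to 3 combination doses and possibly Part 2, which the Grade 3 text already requires.

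No SAP change is needed: SAP 7.4.1 already plans a by-subject listing of infusion details and dose changes, and SAP 7.4.2.2 summarizes interruptions with their reasons. In the same amendment the sponsor may tidy the Arm A wording, which speaks of raising to 50% a rate already restarted at 50%. That is optional and editorial, since the intended cap is clear.

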7.5 Preparation/Handling/Storage/Accountability

The investigational product should be stored in a secure area according to local regulations. It is the responsibility of the investigator to ensure that investigational product is only dispensed to study Participants. The investigational product must be dispensed only from official study sites by authorized personnel according to local regulations.

The product storage manager should ensure that the study treatment is stored in accordance with the environmental conditions (temperature, light, and humidity) as determined by BMS. If concerns regarding the quality or appearance of the study treatment arise, the study treatment should not be dispensed and contact BMS immediately.

Study treatment not supplied by BMS will be stored in accordance with the package insert.

Investigational product documentation (whether supplied by BMS or not) must be maintained that includes all processes required to ensure drug is accurately administered. This includes documentation of drug storage, administration and, as applicable, storage temperatures, reconstitution, and use of required processes (e.g., required diluents, administration sets).

- Further guidance and information for final disposition of unused study treatment are provided in [Appendix 2](#) and Study Reference Manual.

[REDACTED]

7.6 Treatment Compliance

Treatment compliance will be monitored by drug accountability as well as the participant's medical record and electronic case report form (eCRF).

[REDACTED]

7.7.1 Prohibited and/or Restricted Treatments

Prohibited and/or restricted medications taken prior to study treatment administration in the study are described below. Medications taken within 4 weeks prior to study treatment administration must be recorded on the CRF.

The following medications are prohibited during the study (unless utilized to treat a drug related adverse event):

- Immunosuppressive agents
- Immunosuppressive doses of systemic corticosteroids (except as stated in Section 7.7.2).
- Any concurrent anti-neoplastic therapy (ie, chemotherapy, hormonal therapy, immunotherapy, extensive, non-palliative radiation therapy, or standard or investigational agents for treatment of the disease under study).

[REDACTED]

7.7.2 Permitted Therapy

Participants are permitted the use of topical, ocular, intra-articular, intranasal, and inhalational corticosteroids (with minimal systemic absorption). Adrenal replacement steroid doses > 10 mg

daily prednisone are permitted. A brief (less than 3 weeks) course of corticosteroids for prophylaxis (eg, contrast dye allergy) or for treatment of non-autoimmune conditions (eg, delayed-type hypersensitivity reaction caused by a contact allergen) is permitted.

7.7.3 Other Restrictions and Precautions

Participants with a condition requiring systemic treatment with either corticosteroids (> 10 mg daily prednisone equivalent) or other immunosuppressive medications within 14 days of treatment assignment are excluded. Inhaled or topical steroids, and adrenal replacement steroid doses > 10 mg daily prednisone equivalent, are permitted in the absence of active autoimmune disease.

7.8 Treatment After the End of the Study

At the conclusion of the study, participants who continue to demonstrate clinical benefit will be eligible to receive BMS supplied study treatment for the maximum treatment duration specified in the protocol. Study treatment will be provided via an extension of the study, a rollover study requiring approval by responsible health authority and ethics committee or through another mechanism at the discretion of BMS.

BMS reserves the right to terminate access to BMS supplied study treatment if any of the following occur: a) the study is terminated due to safety concerns; b) the development of nivolumab, ipilimumab, and/or BMS-986237 is terminated for other reasons, including but not limited to lack of efficacy and/or not meeting the study objectives; c) the participant can obtain medication from a government sponsored or private health program. In all cases BMS will follow local regulations

8 DISCONTINUATION CRITERIA

8.1 Discontinuation from Study Treatment

Participants MUST discontinue investigational product (and non-investigational product at the discretion of the investigator) for any of the following reasons:

- Participant's request to stop study treatment. Participants who request to discontinue study treatment will remain in the study and must continue to be followed for protocol specified follow-up procedures. The only exception to this is when a participant specifically withdraws consent for any further contact with him/her or persons previously authorized by participant to provide this information
- Any clinical adverse event (AE), laboratory abnormality or intercurrent illness which, in the opinion of the investigator, indicates that continued participation in the study is not in the best interest of the participant
- Termination of the study by Bristol-Myers Squibb (BMS)
- Loss of ability to freely provide consent through imprisonment or involuntarily incarceration for treatment of either a psychiatric or physical (eg, infectious disease) illness.

Refer to the Schedule of Activities for data to be collected at the time of treatment discontinuation and follow-up and for any further evaluations that can be completed

In the case of pregnancy, the investigator must immediately notify the BMS Medical Monitor/designee of this event. In most cases, the study treatment will be permanently discontinued in an appropriate manner (eg, dose tapering if necessary for participant safety). Please call the BMS Medical Monitor within 24 hours of awareness of the pregnancy. If the investigator determines a possible favorable benefit/risk ratio that warrants continuation of study treatment, a discussion between the investigator and the BMS Medical Monitor/designee must occur.

All participants who discontinue study treatment should comply with protocol specified follow-up procedures as outlined in [Section 2](#). The only exception to this requirement is when a participant withdraws consent for all study procedures including post-treatment study follow-up or loses the ability to consent freely (ie, is imprisoned or involuntarily incarcerated for the treatment of either a psychiatric or physical illness).

If study treatment is discontinued prior to the participant's completion of the study, the reason for the discontinuation must be documented in the participant's medical records and entered on the appropriate case report form (CRF) page.

